3.1 Overview of Experimental Design

The overarching aim of this project was to compare the traditional recommendation of immediate post-exercise protein consumption with nighttime pre-sleep protein intake during 12 weeks of resistance training on functional and cognitive adaptations in older adults. To achieve this, our design contained three groups who performed the same 12-week RET program two times per week and: 1) Consumed protein immediately post-exercise (Post-ex), 2) Consumed protein 30 minutes prior to sleep (Pre-sleep), or 3) Did not consume additional protein – exercise only (Ex only). Baseline total kilocalories (kcal) and protein intake were monitored to ensure no significant differences among groups occurred. The dependent variables consisted of pre- to post-intervention changes in body composition (i.e. lean mass, fat mass, and percent body fat), functional capacity (i.e. SPPB), nitrogen balance, free plasma insulin-like growth factor 1 (IGF-1), profile of mood states, and sleep evaluation, and digit symbol substitution and pattern comparison. Pre-, mid-, and post-intervention 1-RM, muscular power, and muscle thickness were assessed to determine the time course of muscular adaptations and appetite changes.

The pre-intervention measures took place over 2-3 days. All participants were instructed to refrain from vigorous physical activity at least 48 hours prior to all pre-testing measurements. On day 1, participants reported to the laboratory in the morning following an overnight fast (participants were encouraged to consume normal water intake) to complete the informed consent process, health history, and physical activity questionnaires. Thereafter, participants completed pre-training assessments including height and weight, baseline blood pressure, psychological and cognitive assessments, blood draw (IGF-1), body composition (DXA or BIA),

muscle thickness, muscular power, and the SPPB. Following the completion of day 1 assessments, participants were provided a 3-day food record, actigraphy watch, and 24-hour urine collection jug (nitrogen balance) to return prior to beginning the RET portion of the study.

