3.3 Participants

Healthy, sedentary (not exercising regularly for the past 6 months), older adult males (N=30; Post-ex n=9, Pre-sleep n=11, Ex only n=10) between the ages of 60-75 years old from the Tallahassee area participated in the study. Health-related exclusion criteria included diagnosis of cardiac or peripheral vascular disease, stroke, kidney dysfunction, metabolic diseases, uncontrolled hypertension, orthopedic limitations, skeletal muscle complications, milk allergy, psychiatric conditions, use of psychotropic drugs or cognitive impairment. Additional exclusion criteria included participation in a structured regular exercise program within the past 6 months, actively attempting to increase or decrease body mass, scoring 26 points or less on the Montreal Cognitive Assessment, and/or body mass index (BMI) of ≥ 35 kg/m². To determine exclusion criteria, all participants completed an informed consent (appendix C), health history questionnaire (appendix E), physical activity questionnaire (appendix F), Montreal Cognitive Assessment (appendix G), and height and weight measurements, prior to any participation in the intervention. Lastly, all participants submitted a physician consent (appendix D) form prior to beginning the exercise training protocol.

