3.8 Sample Size Justification and Statistical Analysis

An a priori analysis was conducted with an effect size F of 0.25 calculated using mean and standard deviations from previously reported changes in LBM in older men (350) with power set to 0.8 and α set to 0.05 for 3 groups and 3 measurements. With an expected dropout rate of 15% (110), a sample size of 36 was adequate and provided an even distribution between groups.

A one-way analysis of variance (ANOVA) was used to analyze baseline differences and total training volume among groups. A 3x2 mixed model ANOVA with group as the between subjects' factor (Post-ex, Pre-sleep, Ex only) and time as the within-subjects factor (pre and post) was performed on all dependent variables except for muscle thickness, 1-RM strength, muscle power, and appetite, where a 3x3 mixed model ANOVA (Post-ex, Pre-sleep, Ex only x pre, mid, post) was used. Pearson product-moment correlation, or Spearman's correlation in the event of normality violation, was used to determine the relationship between changes in free IGF-1 and changes in body composition, muscle thickness, 1-RM strength, muscular power, and cognitive assessments.

Outliers were removed and defined as values outside of the mean \pm 3 standard deviations. Data were tested for normality (Shapiro-Wilk), homogeneity of variances (Levene's test), and sphericity (Mauchly's test) where appropriate. When normality or homogeneity of variances was violated, non-parametric testing or data transformation was performed. For a mixed model ANOVA, if transformation could not correct the violation, original data were analyzed, as there are no non-parametric alternatives. When sphericity was violated, the main time and group x time interactions were interpreted with the Greenhouse-Geisser estimation.

Significance was set at $p \leq 0.05$. Trends were noted for p -values between 0.051-0.10. For significant interactions and main effects, pairwise comparisons with Bonferroni adjustments were conducted (296, 332). Pearson correlation coefficients (r) or Spearman's correlation coefficients (r_s) were interpreted as "negligible" = < 0.30 , "low" = $0.30-0.50$, "moderate" = $0.50-0.70$, "high" = $0.70-0.90$, and "very high" = > 0.90 (244). Percentage change was calculated as $((\text{post value} - \text{pre value}) * 100)$. All analyses were performed with SPSS version 25

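### No outcome is named primary in the supplied text, and about 29 outcomes are each tested at 0.05 with no control of error across them

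*Combined protocol and SAP*

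**What the plan says.** Section 3.1 gives a broad aim, functional and cognitive adaptation, and then a list: "The dependent variables consisted of pre- to post-intervention changes in body composition", followed by function, nitrogen balance, IGF-1, mood, sleep and cognition. Sections 3.2.1 to 3.2.3 spread these over three aims without ranking them. The word primary appears only for exercises (section 3.4).

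Section 3.8 sets one threshold for everything: "Significance was set at $p \leq 0.05". It also notes trends for p-values from 0.051 to 0.10. Each dependent variable gets a 3x2 mixed ANOVA. Muscle thickness, 1-RM, power and appetite get a 3x3 instead. Changes in free IGF-1 are also correlated with changes in five groups of outcomes. The only adjustment described is "For significant interactions and main effects, pairwise comparisons with Bonferroni adjustments were conducted".

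The sample size rests on one variable: "effect size F of 0.25 calculated using mean and standard deviations from previously reported changes in LBM in older men". That variable is not called primary.

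**The concern.** Bonferroni among pairwise comparisons limits error among group or time pairs for a single outcome. The omnibus test that opens the way to those comparisons is run at 0.05 for each outcome separately, so nothing limits the chance that some outcome passes by luck. Without a named primary outcome, the plan gives no rule for deciding which significant interaction answers the question on protein timing. A lone positive among mood, sleep, strength or body-composition measures would have the same standing as a positive on lean mass. Noting trends up to 0.10 widens the room for selective emphasis. The plan does not describe itself as exploratory.

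**Working it through.** **1. The plan's own figure.** Section 3.8 states "power set to 0.8 and α set to 0.05 for 3 groups and 3 measurements", f = 0.25 and a total of 36 with 15% dropout. It states neither the correlation between repeated measures (ρ) nor which effect was powered. I assume ρ = 0.5 and sphericity, and use the noncentral F with λ = f²·N·m/(1−ρ).

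- Group-by-time, m = 3: at N = 35, λ = 0.0625 × 35 × 3 / 0.5 = 13.1 and power is 0.81, against 0.795 at N = 34. Equal groups give 36, but before dropout; 35/0.85 = 41.2, so 42 after it. Over ρ from 0.7 to 0.3 the required N runs from 22 to 48.
- Time main effect, m = 3: N = 28, or 30 in equal groups; 30/0.85 = 35.3, so 36 after dropout.

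The figure of 36 can therefore be reached, but only under assumptions that the text does not state. The multiplicity point does not depend on it.

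**2. Count of outcomes.**

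| Domain (section) | Outcomes |
|---|---|
| Lean mass, fat mass, percent fat (3.1) | 3 |
| Summed muscle thickness (3.7.2) | 1 |
| Leg press and chest press 1-RM (3.7.3.1) | 2 |
| Peak and average power (3.7.3.2) | 2 |
| SPPB: three components and total (3.7.3.3) | 4 |
| Digit symbol, pattern comparison (3.7.4) | 2 |
| Hunger, satiety, desire to eat (3.7.5.1) | 3 |
| POMS: six domains and total (3.7.5.2) | 7 |
| Sleep time, latency, efficiency (3.7.5.3) | 3 |
| Nitrogen balance (3.7.6) | 1 |
| Free IGF-1 (3.7.7) | 1 |
| **Total** | **29** |

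Testing the three thickness sites as well would give 32. Taking only the items listed under the aims in section 3.2 gives 10 + 5 + 2 = 17. Group and time main effects are left out of the count; time effects are expected with training.

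**3. Error across the group-by-time tests, all nulls true.**

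- Expected false positives: 29 × 0.05 = 1.45. This holds for any correlation between outcomes.
- At least one, if independent: 1 − 0.95^29 = 0.774. With 32 tests it is 0.806; with 17 it is 1 − 0.95^17 = 0.582.
- At the trend threshold, 29 independent tests: 1 − 0.90^29 = 0.953.

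**4. Allowing for correlation.** The documents give no correlations between outcomes, so these are assumptions. Null changes in 29 outcomes were simulated in groups of 9, 11 and 10 (section 3.3), with a one-way ANOVA on change and 20,000 runs:

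| Assumed correlation | Chance of at least one |
|---|---|
| 0.2 throughout | 0.72 |
| 0.3 throughout | 0.67 |
| 0.5 throughout | 0.53 |
| 0.7 throughout | 0.36 |
| 0.7 within domains, 0.2 between | 0.64 |

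The simulation treats every outcome as a two-time-point change, which simplifies the 3x3 outcomes.

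**5. What adjustment would cost.** Group-by-time power in the 3x2 design at N = 30, f = 0.25 and ρ = 0.5 is 0.64 at α = 0.05 (0.49 to 0.86 for ρ from 0.3 to 0.7). At 0.05/29 = 0.0017 it falls to 0.17 (0.09 to 0.39). For a Pre-sleep versus Post-ex contrast alone (11 + 9 = 20), again taking f = 0.25, λ = 0.0625 × 20 × 2 / 0.5 = 5.0 and power is 0.56 (0.43 to 0.78).

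**The case against.** **Independence fails by construction.** The POMS total is computed from its domains, the SPPB total is the sum of its parts, the three body-composition figures come from one measurement, and peak and average power come from the same trials. This stands. The 77% can serve only as an upper illustration. It does not touch the expected count of 1.45, and the chance of at least one falls below one half only with a correlation of 0.7 across all 29 outcomes. That is hard to believe across mood, sleep, strength and IGF-1.

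**Lean mass is primary in effect, because it supplied the effect size.** This stands in part: it makes lean mass the natural candidate. But the text never gives it that status, the stated aim is functional and cognitive, and the calculation assumes three measurements where body composition has two.

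**Adjusting across everything would destroy power.** This is true of Bonferroni over 29. It argues for one primary test rather than for no control. Holm within each aim would leave about 1 − 0.95³ = 14% across three independent aims. Its first step in Aim 1 (12 outcomes, 0.05/12) would have power of about 0.25 under the assumptions above. It would also leave the IGF-1 correlations without a family.

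**A reader might add the roughly 10 IGF-1 correlations and quote 1 − 0.95^39 = 86%.** The documents do not support that as the chance of a false answer on protein timing. The correlations compare no groups, and they all share one variable, so they are not independent tests. They are unadjusted, but they form a separate set.

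**Conclusion.** The point holds. Followed as written, the plan leaves error across about 29 group-by-time tests uncontrolled. With all nulls true, 1.45 false-positive interactions are expected. The chance of at least one is 77% at the upper end and roughly 53–72% for assumed correlations of 0.5 to 0.2. These figures rest on one interaction test per outcome and on the count above; the correlations are assumed.

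Two limits apply. First, the absence of a primary outcome is a statement about the supplied text, which begins at section 3.1. Second, a reader might infer that a chance result has been presented as the trial's answer, or that a given positive result is false. The supplied text contains no outcome results and supports neither inference; it shows only that the plan does not guard against this.

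**What to change.** In section 3.8:

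1. Name one primary test that alone carries α = 0.05. Lean mass is the natural candidate, through the Pre-sleep versus Post-ex difference in pre-to-post change. Say that this contrast, and not the three-group interaction, is the primary test.
2. Deal with the switch from DXA to BIA after 8 scans (section 3.7.1). Each participant's pre and post values should come from the same device, and the analysis should account for device. State how many participants fall in each case.
3. State that the choice is post hoc unless an earlier record documents it. The text is in the past tense and already reports "N=30; Post-ex n=9, Pre-sleep n=11, Ex only n=10".
4. Report all other outcomes and all IGF-1 correlations as exploratory, with estimates and 95% confidence intervals and no claims of significance or trend.

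The cost is wording, plus the device check for lean mass. Fewer results can be called significant, and the primary contrast has only modest power (about 0.56 under the assumptions above). A primary named after the data are in cannot fully restore error control, so the reporting in step 4 is the part of the remedy that does not depend on when the choice was made.

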3.7.2 Muscle Thickness

Muscle thickness was assessed via ultrasonography (HD11 XE, Philips, Netherlands) using a linear-array transducer with 3-12 MHz (L 12-3, Philips, Netherlands) and was used as an index of muscle hypertrophy for the quadriceps musculature. This technique has been previously employed to measure the hypertrophic response to RET (182) and has compared favorably to magnetic resonance imaging for muscle size (288). Ultrasound scans took place during pre-, mid-, and post-testing time points in the supine position after participants had been resting for 10 minutes to allow for any fluid shift to occur. During this time, specific anatomical locations were identified and marked with a water-soluble pen at 50% of distance between the greater trochanter and the lateral condyle of the femur and 50% of the distance between the anterior superior iliac spine and the superior border of the patella. These anatomical locations allowed for imaging of the vastus lateralis, vastus intermedius, and rectus femoris muscles (1, 146).

All ultrasound scans were completed by the same person and conducted on the right side of the body. Prior to each scan, a water-soluble transmission gel was applied to the transducer for optimal acoustic contact. Furthermore, minimal pressure was applied to the transducer to limit compression of tissues. Muscle thickness was measured as the distance (cm) from the adipose-muscle interface to the muscle-fascicle or muscle-bone interface. The values from the three sites were summed together for a total muscle thickness measure. Muscle thickness test-rest reliability measured by intraclass correlation coefficients (model 3,1) for the muscle groups were: vastus lateralis, 0.977 (95% confidence intervals: 0.835, 0.997); rectus femoris 0.995 (95% confidence intervals: 0.957, 0.999); vastus intermedius 0.977 (95% confidence intervals: 0.834, 0.998).

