Interpretation of the SPPB outcomes was in accordance with previously established values (140). Briefly, each SPPB test was scored on a 0-4 scale, based upon time or completion of the task, with lower values indicating worse performance and vice versa. Scoring for the balance portion of the SPPB will consisted of: 1 point for maintaining the side-by-side position for 10 seconds, 1 point for maintaining the semi-tandem for 10 seconds, and 1 point for maintaining the full-tandem position between 3–9.99 seconds or 2 points for maintaining the full-tandem position for 10 seconds. If the participant could not maintain the side-by-side position for 10 seconds, the balance portion was scored 0. The gait speed test scoring was based upon the amount of time to walk 4 meters at a normal pace using the following cut off times: 1 point for times greater than 8.70 seconds, 2 points for times between 6.21–8.69 seconds, 3 points for times between 4.82–6.20 seconds, and 4 points for times less than 4.82 seconds. If the participants could not complete the 4-meter walk, then the gait speed test was scored as 0. Lastly, the 5-chair stand scoring was also based upon cut off times including: 1 point for times greater than 16.70 seconds, 2 points for times between 13.70–16.69 seconds, 3 points for times between 11.20–13.69 seconds, and 4 points for times less than 11.19 seconds. If the participant could not complete a sit-to-stand task, then the 5-chair stand test was scored as 0. Once all portions of the SPPB were completed the scores from all 3 tests were summed together for a total score, with 12 being the highest possible score.

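### The written definition of percentage change in section 3.8 omits division by the pre value, so the rule as stated does not give a percentage

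*Combined protocol and SAP*

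**What the plan says.** The statistical part of section 3.8 gives one definition of percentage change: "Percentage change was calculated as $((\text{post value} - \text{pre value}) * 100". The formula closes there, with nothing beneath or after the difference.

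The pre and post values it refers to are the assessments that feed the ANOVAs. The two-time-point model, with "time as the within-subjects factor (pre and post) was performed on all dependent variables except for muscle thickness, 1-RM strength, muscle power, and appetite", uses pre and post; the four excepted outcomes also have a mid value.

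The outcomes are on very different scales. Section 3.7.2 gives a length: "Muscle thickness was measured as the distance (cm) from the adipose-muscle interface to the muscle-fascicle or muscle-bone interface". Section 3.7.3.3 gives a bounded score, "summed together for a total score, with 12 being the highest possible score". Nitrogen balance (section 3.7.6) is intake minus losses, and the appetite VAS (section 3.7.5.1) starts at 0.

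Section 3.8 also plans correlations between changes in free IGF-1 and changes in body composition, muscle thickness, strength, power and cognition. It does not say whether those changes are absolute or percentage.

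**The concern.** A percentage change is a difference relative to a baseline. It has no unit, which is what allows it to be compared between participants and between outcomes. The printed rule has no baseline term, so its result keeps the outcome's unit, scaled by 100. It would change if the same measurement were recorded in another unit.

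This is a stated computational rule, not a detail left open. Anyone who reproduces the analysis from section 3.8 would get values that are not percentages, and the size of the discrepancy would differ by outcome and by participant. For many outcomes the result would be absurd and easily caught. For an outcome held as a proportion it could look plausible and pass unnoticed.

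**Working it through.** **Inputs.** The formula is from section 3.8. The documents give no pre or post values and no percentage-change result, so there is no figure of the plan's own to reproduce. All pre and post values below are assumed, for illustration only.

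**Algebra.**

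- Stated rule: S = (post − pre) × 100
- Percentage change: P = ((post − pre) / pre) × 100
- Hence S = P × pre. The two agree only when pre = 1 or when nothing changes.

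**Assumed examples.**

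| Outcome | Pre → post | Stated rule S | Percentage change P | S / P |
|---|---|---|---|---|
| Lean mass, kg | 60 → 61 | (61 − 60) × 100 = 100 | 1/60 × 100 = 1.67% | 60 |
| Muscle thickness, cm | 6.0 → 6.3 | 0.3 × 100 = 30 | 0.3/6.0 × 100 = 5.0% | 6 |
| Leg press 1-RM, kg | 100 → 125 | 25 × 100 = 2500 | 25/100 × 100 = 25% | 100 |
| SPPB total | 11 → 12 | 1 × 100 = 100 | 1/11 × 100 = 9.09% | 11 |

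In each row the ratio equals the pre value, as the algebra requires.

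**Dependence on the unit.** The same muscle-thickness gain recorded in mm (60 → 63) gives S = 300 instead of 30, while P stays at 5.0%. The same lean-mass gain in g (60000 → 61000) gives S = 100000 instead of 100, while P stays at 1.67%.

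**A case that would not look wrong.** Section 3.7.5.3 describes sleep efficiency as a ratio. If it is held as a proportion, an assumed rise from 0.80 to 0.84 gives S = 0.04 × 100 = 4, against P = 0.04/0.80 × 100 = 5%. The 4 is a percentage-point difference and could be read as a percentage change.

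**Where the rule could enter the planned analyses.**

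- One-way ANOVA: used for baseline differences and total training volume. Percentage change is not mentioned.
- Mixed ANOVAs: pre, mid where measured, and post are levels of the time factor. Percentage change is not mentioned.
- Free IGF-1 correlations: the type of change is not stated. S is the absolute change times a constant, so it gives the same Pearson or Spearman coefficient as absolute change. P divides by each man's own baseline and can give a different coefficient. If percentages were intended here, the missing denominator would matter beyond description; if absolute changes were intended, it would not.

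**The case against.** The strongest reply is that this is a slip of description with no shown consequence. The document is written in the past tense, so it describes work already done. A spreadsheet returning 2500 as a leg press percentage would have been noticed at once, and it is at least as plausible that the division was made and left out of the sentence. No analysis is stated to depend on the formula, and section 3.8 closes by saying that data are shown as means and standard deviations unless otherwise stated.

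Most of this stands as a limit on consequence. A reader might infer that every outcome shown as percentage change has been misreported. The documents do not support that: they contain no percentage-change result, name no outcome to be presented that way, and do not show what was computed. A reader might also infer that the ANOVA p-values are affected, and nothing in section 3.8 supports that either. What remains is that the written rule is wrong.

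A second reply is that a denominator was lost when the PDF was read. This cannot be excluded. It is not shown, however: the brackets in the formula balance, there is no gap, and the nitrogen balance equation in section 3.7.6 kept its division by 6.25.

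A third reply is that division by the pre value cannot be applied to every outcome. That is correct. Nitrogen balance can be zero or negative at baseline, which makes the ratio undefined or gives it a misleading sign. A VAS rating can be 0. The correction has to be restricted accordingly.

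**Conclusion.** The point holds as an error in the stated rule. As written, section 3.8 defines 100 times the raw difference, which is the true percentage change multiplied by the pre value. The size of the discrepancy is therefore the baseline itself: a factor of 60 for an assumed lean mass of 60 kg, and a factor of 11 for an assumed SPPB total of 11.

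The algebra needs no assumption beyond reading the formula as printed; only the worked values are assumed. The finding does not reach any reported result, the ANOVAs, or the sample size. Whether it reaches the free IGF-1 correlations depends on a choice that the plan does not state.

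**What to change.** 1. Replace the formula in section 3.8 with ((post value − pre value) / pre value) × 100, and limit it to outcomes whose baseline is strictly positive.
2. For outcomes whose baseline can be zero or negative, such as nitrogen balance and the appetite VAS, report absolute change.
3. State whether the changes in the free IGF-1 correlations are absolute or percentage.
4. Check which formula was used in the actual calculations, and recompute any percentage produced with the printed one.

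It would also help to say whether a group figure is the mean of individual percentages, but that is a clarification and not part of the error.

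The cost is a line or two of text and a check of the descriptive output. A re-run is needed only if the printed formula was in fact used, and it would extend to the correlations only if step 3 shows that they were based on percentages.
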